3.0 STUDY DESIGN

This is a prospective, multi-center, single arm, Phase 2 study of human retinal progenitor cells (jCell) for the treatment of retinitis pigmentosa (RP). The study will include only subjects previously treated with jCell.

To assess reinjection of a previously treated eye, subjects who have previously been treated with jCell and desire a second treatment in the same eye will be enrolled. Subjects must have completed at least 12 months of follow up since the prior injection of jCell. Subjects who have had both eyes previously treated with jCell will only have one eye retreated; the eye to be retreated will preferably be the better seeing eye, but exceptions may be made by the study investigator, taking into consideration BCVA, prior response to treatment, and any other medical conditions that may indicate which eye is the best candidate for retreatment. Subjects will be followed for 12 months for safety and efficacy.

As noted above, subjects may be asked to undergo additional testing at the jCyte low vision facility to assess the characteristics of the jCell aggregate inside the eye (size and structure) and retinal sensitivity following treatment. These are exploratory assessments, and any/all may be discontinued if they are determined to be difficult to conduct or the results appear to be of little value in understanding the course of the injected cells and/or changes in retinal

sensitivity over time. Participation in these exploratory assessments is not required for study participation.

3.1 Study Population

Subject treatment with jCell is primarily to assess safety of retreatment and is focused solely on subjects who have previously received jCell and desire to be retreated in the same eye. Study subjects will be screened for eligibility and informed consent obtained. Eligible subjects will receive a single injection of 6×10^6 jCell into one previously treated eye. If both eyes were previously treated, the preference is to treat the better eye. However, the study Investigator may select the poorer seeing eye taking into consideration BCVA, prior response to treatment, and any other medical conditions that may indicate which eye is the best candidate for retreatment. Strong rationale must be provided if the decision is made not to treat the better seeing eye. The study investigator must determine that there are no unforeseen or unusual safety issues that would preclude the retreatment. Following treatment, subjects will be followed for at least 12 months to assess safety and efficacy.

3.2 Endpoints

3.2.1 Efficacy Endpoints

Efficacy will be assessed as secondary endpoints in this study and will include for all subjects vision parameters of Best Corrected Visual Acuity (BCVA) as assessed at the clinical site at all visits, as well as mobility (maze navigation), contrast sensitivity (CS), and visual fields (VF) at baseline and at six and 12 months after treatment as assessed at the jCyte low vision facility.

3.2.2 Safety Endpoints

The main criteria that will be used to assess safety include:

- Incidence and severity of treatment-emergent adverse events (TEAE)
- Safety visual assessments: slit lamp and fundus exam, IOP

Blood samples will be collected from subjects at baseline and at designated times post-treatment to assess immunogenicity of the injected cells (PRA, DRA).

3.3 Study Duration

The overall duration of the study is anticipated to be approximately two years. This assumes subjects will be enrolled and treated within one year or less and a follow up of 12 months for each subject. The study will be considered to have started when the first site is initiated.

3.4 Early Study Termination

The Sponsor may terminate this study at any time. Reasons for termination may include but are not limited to, the following:

- The incidence or severity of AEs in this or other studies point to a potential health hazard for study subjects.
- Insufficient subject enrollment.
- Any information becoming available during the study that substantially changes the expected benefit-risk profile of the investigational drug.

4.0 SUBJECT SELECTION

4.1 Inclusion Criteria

The following conditions must be met before a previously treated subject may be enrolled.

- 1. Willing to give written informed consent, able to make the required study visits and follow study protocol instructions.
- 2. Completed the 12 months of follow up in the subject's most recent jCell study and did not withdraw from the study for any reason.
- 3. Adequate organ function:
 - blood counts (hematocrit, Hgb, WBC, platelets and differential) within normal range, or if outside of normal range, not clinically significant as judged by the investigator
 - o liver function: alanine transaminase [ALT] and aspartate transaminase [AST]
 ≤2 times the upper limit of the normal range
 - total bilirubin \leq 1.5 times the upper limit of the normal range
 - \circ renal function: serum creatinine ≤ 1.25 times the upper limit of the normal range
- 4. A female patient of childbearing potential (not surgically sterilized and less than one year postmenopausal) must have a negative pregnancy test (urine human chorionic gonadotropin) at entry (prior to injection) and must have used medically accepted contraception for at least one month prior to treatment. Women of childbearing potential and men must be advised to use a medically accepted method of contraception for at least 12 months following treatment.

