⁶ subjects may have some or all of the following assessments at the jCyte Low Vision Facility at the indicated timepoints: ultrasound imaging [ultrasound biomicroscopy (UBM), A-scan, and/or B-scan], slit lamp biomicroscopy with photography/videography using gonioscopy lens, OCT imaging of jCells, retinal sensitivity with FST of both eyes separately (monocular testing, FST only performed at Baseline, M3, M6, and M12) *Day -30 to 0. Does not need to be repeated if Day 0 is within 30 days of screening.

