6.2 Baseline

The assessments (indicated by an asterisk*) do not need to be repeated if Day 0 (treatment day) is within 30 days of screening. Subjects should be advised to discontinue daily aspirin or clopidogrel regimens for 5 days prior to study treatment.

Performed at clinical study site at baseline

- a. Updated medical history and physical exam*, including height, weight, and detailed ocular medical history including any previously undocumented history of eye diseases or disorders other than RP
- b. vital signs
- c. pregnancy test, if female*
- d. hematology [CBC, platelet, differential, hemoglobin, hematocrit]*
- e. blood chemistries*, not limited to, but must include AP, ALT, AST, BUN, Cr, total bilirubin, serum electrolytes, glucose, calcium, phosphate, albumin and total protein
- f. urinalysis*
- g. slit lamp, fundus exam
- h. Optos photography
- i. BCVA
- j. IOP
- k. OCT (performed at site and sent to central reading lab for analysis)
- 1. blood sample for Ab testing

Performed at jCyte low vision facility at baseline

- m. VF
- n. Contrast Sensitivity
- o. Mobility test
- p. Optional exploratory ophthalmic imaging: ultrasound imaging (ultrasound biomicroscopy, ultrasound A- and B-scan), additional variants of slit lamp biomicroscopy with photography/videography using gonioscopy lens, optical coherence tomography (OCT) of jCells and/or retinal sensitivity with full-field sensitivity threshold testing (FST)

6.3 Day 0

Before administration of jCell (Day 0)

- a. vital signs, within 15 minutes prior to injection
- b. BCVA
- c. IOP

After administration of a single intravitreal dose of jCell

- a. exact dose and time of injection ; any dose interruption must be documented
- b. vital signs at 15 and 60 minutes after treatment or until returned to pre-treatment levels
- c. intraocular pressure by tonometry post-treatment must be ≤30 mm Hg prior to patient release
- d. verify basic vision by lights, hand motions and fingers, depending upon individual patient's baseline prior to patient release
- e. con meds
- f. adverse events

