6.3.7 End of Treatment (Month 12) or Early Termination Visit +/- 10 days

Performed at clinical study site 12 months post-treatment

- a. MH and physical exam, including weight and height
- b. vital signs
- c. pregnancy test (if applicable)
- d. CBC, platelet, differential, hemoglobin, hematocrit
- e. blood chemistries, not limited to, but must include AP, ALT, AST, BUN, Cr, total bilirubin, serum electrolytes, glucose, calcium, phosphate, albumin and total protein
- f. urinalysis
- g. slit lamp and fundus exam
- h. Optos photography
- i. BCVA
- j. IOP
- k. OCT (performed at site and sent to central reading lab for analysis)
- l. con meds
- m. adverse events

Performed at jCyte low vision facility 12 months post-treatment

- n. VF
- o. Contrast Sensitivity
- p. Mobility test
- q. optional exploratory ophthalmic imaging: ultrasound imaging (UBM, A- and Bscan), additional variants of slit lamp biomicroscopy with photography/videography using gonioscopy lens, OCT of jCells and/or retinal sensitivity with FST.

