7.1.3 Clinical Laboratory Tests

Blood samples for clinical laboratory tests will be taken as indicated in Table 2.

Hematology – full blood count including red blood cell (RBC) count, hemoglobin, hematocrit, white blood cell (WBC) count with differential and platelet count; neutrophils, lymphocytes, monocytes, eosinophils, basophils.

Biochemistry – alanine aminotransferase (ALT), aspartate aminotransferase (AST), alkaline phosphatase (AP), blood urea nitrogen (BUN), creatinine, total bilirubin, serum electrolytes, glucose, calcium, phosphate, albumin and total protein

Urinalysis – pH, protein, ketones, glucose, bilirubin, blood, urobilinogen, specific gravity by dipstick and microscopy if any findings are abnormal.

Pregnancy A urine sample will be collected for a pregnancy test at screening for female subjects of childbearing potential to test for pregnancy. If this is found to be positive, it will be followed up with a serum pregnancy test.

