10.7 Investigational Product and Label Codes

The investigational product is jCell. Frozen vials of jCell (hRPC) drug product are provided to the qualified dose preparation facility by [name] of the GMP Facility at UC Davis, where the cells were manufactured and are currently cryopreserved.

When a study subject has been scheduled for treatment, the qualified dose preparation site will prepare the patient dose according to a standard procedure. Frozen cells are thawed and cultured 40-48 hours prior to injection. Following successful culture and testing, 65 μ l of cell suspension containing 6 million human retinal progenitor cells suspended in clinical grade medium (BSS PLUS) will be provided by the dose preparation facility to the clinical site, on ice, with targeted administration to the patient within 4 hours of cell harvest. Patients will undergo topical anesthesia prior to injection of the cells.

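### No pregnancy test is scheduled on the day of injection, so a woman of childbearing potential can be treated on a negative urine result up to 30 days old

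*Protocol*

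**What the plan says.** Criterion 4 in Protocol 4.1 (repeated in the synopsis) sets two conditions before treatment for women of childbearing potential. One is that the woman "must have a negative pregnancy test (urine human chorionic gonadotropin) at entry (prior to injection"). The other is at least one month of accepted contraception before treatment. No number of hours or days between test and injection is stated.

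Timing is set elsewhere in the protocol:

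- **Table 2 (section 5.1)** marks the pregnancy test at Screening, at Baseline with an asterisk, and at Month 12 or Early Termination. The Day 0 cell is empty.
- **The asterisk footnote to Table 2** reads "Day -30 to 0. Does not need to be repeated if Day 0 is within 30 days of screening".
- **Section 6.2** lists "pregnancy test, if female" among the asterisked baseline items, which "do not need to be repeated if Day 0 (treatment day) is within 30 days of screening".
- **Section 6.3** gives three checks before administration on Day 0: "vital signs, within 15 minutes prior to injection", BCVA and IOP.
- **Section 6.3.7** lists "pregnancy test (if applicable") at Month 12 or Early Termination.
- **Section 7.1.3** describes one urine test only: "A urine sample will be collected for a pregnancy test at screening for female subjects of childbearing potential". A serum test follows if the urine test is positive.

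**The concern.** Criterion 4 exists to keep a pregnant woman from receiving the product, which is a live suspension of allogeneic cells of human fetal origin. Pregnancy status can change between screening and treatment, and a negative test says nothing about a conception after it. The treatment is one injection that cannot be withdrawn, so only a check made before it can prevent exposure. The next scheduled test is at Month 12 or Early Termination.

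The protocol repeats vital signs, acuity and pressure on Day 0 but not this entry condition. What is at stake is subject safety. No endpoint, estimate or analysis in the SAP depends on it; pregnancy results go to a listing only (SAP 13.4).

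**Working it through.** The plan states no figure to reproduce. The question is how old the qualifying result can be at injection if every scheduled step is followed.

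**Inputs**

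- Criterion 4 (Protocol 4.1): negative urine hCG before injection; no maximum interval.
- Table 2 footnote and section 6.2: baseline test waived if Day 0 is within 30 days of screening; otherwise its window is Day -30 to Day 0.
- Table 2 and section 6.3: no pregnancy test on Day 0.
- Sample size (synopsis; SAP 5): 25-30 subjects.
- Cell preparation (Protocol 10.7): "Frozen cells are thawed and cultured 40-48 hours prior to injection".

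**Age of result = day of injection - day of test**

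| Route | Test used | Earliest permitted day | Age at injection |
|---|---|---|---|
| A: screening 30 days or less before Day 0, baseline test waived | Screening | Day -30 | up to 0 - (-30) = 30 days |
| B: baseline test done | Baseline | Day -30 | 0 to 30 days |
| With a Day 0 test added | Day 0 | Day 0 | 0 days |

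The maximum is 30 days on both routes. Route B can give a same-day result, because the window runs to Day 0, but nothing requires it.

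**Is there a contradiction?** No. A negative screening test satisfies criterion 4 as worded. The criterion leaves the interval open and the schedule fills it with 30 days.

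**Section 7.1.3.** It omits the baseline and Month 12 tests that Table 2, 6.2 and 6.3.7 schedule. This is an editorial omission and carries no weight in the conclusion.

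**Upper bound on added testing.** 30 subjects × 1 test = 30 tests, if every subject were a woman of childbearing potential. The documents do not give the actual number.

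**The case against.** The strongest reply is that the protocol does set a limit. An eligibility criterion that states a requirement, with the schedule stating its timing, is ordinary structure; the limit is 30 days, no document here demands a shorter one, and a preference for less is a matter of judgement. The required month of contraception covers essentially the same interval, so the test and contraception work as a pair. The investigator must also rule out unforeseen safety issues before retreatment (section 3.1). Section 5.1 refers to the study procedure manual for patient preparation, and that manual might already call for a same-day test. A Day 0 test comes after the cells have been thawed, so a positive result wastes a dose. Finally, the planned study period ended in Q3 2022 and the SAP is dated 09 Nov 2022, so dosing was probably complete.

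Much of this is fair. It is a gap, not an inconsistency. The documents describe no fetal hazard from this injection, and the residual risk is largely confined to contraceptive failure and to a pregnancy too early to detect when the test was done. An amendment may now help only later dosing or a successor protocol.

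The central point stands. Criterion 4 asks for contraception and a test, so one was not meant to replace the other. Investigator judgement cannot detect an early pregnancy without a test. The manual was not available, and an eligibility safeguard belongs in the protocol that the review board approves.

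**Conclusion.** The concern holds as a low-cost safety improvement that should be made. Followed exactly, the schedule permits injection on a negative urine result up to 30 days old, and it schedules no pregnancy test on Day 0.

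This rests on reading the asterisk rule as applying to the pregnancy test, which Table 2 and section 6.2 both mark, and on the study procedure manual not adding a later test. The number of women exposed to the gap cannot be estimated from the documents, so no probability of an exposed pregnancy is offered. Confidence is moderate because of the unseen manual.

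**What to change.** 1. Add a urine hCG test for women of childbearing potential to the pre-injection list in section 6.3 and to the Day 0 column of Table 2.
2. In criterion 4 (section 4.1 and the synopsis), require the Day 0 result to be negative before injection.
3. Align section 7.1.3 with the tests actually scheduled, including Day 0 and Month 12.
4. If the procedure manual already requires a Day 0 test, carry that requirement into the protocol.

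The baseline test and its 30-day waiver can stay as they are.

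**Cost.** A short amendment and one dipstick per eligible woman at a visit already held, at most 30 in all. A positive result on Day 0 would waste one prepared dose. Testing just before the thaw would save that dose, but the result would then be at least 40-48 hours old at injection. It could be added as an extra check, but the Day 0 test should be the one that decides. Even a same-day urine test can miss a very early pregnancy, so the contraception requirement must remain.

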4.2 Exclusion Criteria

Patients previously treated with jCell will be excluded from this study if they meet any of the following criteria:

1. Malignancy, end-stage major organ disease (heart failure, significant arrhythmias, stroke or transient ischemic attacks, diabetes, immunosuppressive or autoimmune state, major psychiatric disorder, epilepsy, thyroid disease, COPD, renal failure, or any chronic systemic disease requiring continuous treatment with systemic steroids, anticoagulants or immunosuppressive agents.

- 2. History of eye disease other than RP that impairs visual function, including retinal vascular disease, elevated intraocular pressure/glaucoma, severe posterior uveitis, clinically significant macular edema, media opacity precluding visual exam, amblyopia and/or longstanding constant strabismus, as well as patients who require other intravitreal therapies
- 3. Allergy to penicillin or streptomycin.
- 4. Adverse reaction to DMSO.
- 5. Unable or unwilling to undergo pupil dilation, topical anesthesia or any protocolrequired procedure.
- 6. Women who are nursing or who are planning to nurse during the 12 months that would follow study treatment.
- 7. Any circumstance that in the opinion of the investigator, would interfere with participation in, or compliance with the study protocol
- 8. Treatment with corticosteroids (systemic, periocular or intravitreal) or any other non-approved, experimental, investigational or neuroprotectant therapy (systemic, topical, intravitreal) in either eye within 90 days of planned second injection.
- 9. Cataract surgery within three months prior to treatment or anticipated to need cataract surgery within a year of treatment

4.3 Subject Withdrawal Criteria

Subjects may withdraw from the study at any time. Subjects may be discontinued from the study for any of the following reasons:

- Withdrawal of consent by the subject
- Lost to follow-up

The investigator may also withdraw a subject at any time at his/her discretion. The sponsor reserves the right to terminate the study or withdraw any subject from the study for any reason at any time.

In addition, the sponsor reserves the right to temporarily suspend or prematurely discontinue this study either at a single site or at all sites at any time and for any reason. If such action is taken, the sponsor will discuss this with the investigator (including the reasons for taking such action) at that time. The sponsor will promptly inform all other investigators and/or institutions conducting the study if the study is suspended or terminated for safety reasons, and will also inform the regulatory authorities of the suspension or termination of the study and the reason(s) for the action. If required by applicable regulations, the investigator must inform the IRB promptly and provide the reason for suspension or termination.

4.4 Discontinuation/Withdrawal Procedures

If a subject is withdrawn from the study (i.e., ceases participation in the study prior to completion of the assessments planned in the protocol), the primary reason should be recorded in the case report form (CRF). Investigators should make every effort to capture withdrawal assessments, which will be recorded in the CRF.

The investigator will provide or arrange for appropriate follow-up (if required) for subjects withdrawing from the study and will document the course of the subject's condition.

5.0 TREATMENT PLAN

5.1 Dose and Schedule

At the time informed consent is obtained, qualified subjects will be assigned a study number. All subjects will receive a single intravitreal injection of 6.0×10^6 hRPC into one previously treated eye. After topical anesthesia, a single 65 microliter suspension of cells will be delivered into the vitreous cavity using a 30 g needle. This treatment does not require surgical detachment or manipulation of the retina. The injection procedure itself takes approximately 2 minutes. Following 60 minutes of observation with no serious clinical symptoms or manifestations (IOP < 30 mm Hg and vital signs comparable to pre-treatment), subjects will be released to home on the day of injection. Please refer to the study procedure manual for details of patient preparation and monitoring.

The schedule of observations and assessments during the study is summarized in Table 2.

Table 2 Schedule of Assessme

Timepoint	Scr	BL*	Day 0	Day 1	Day 7 ³	Day 28 ³	M3 ⁴	M6 ⁴	M9 ⁴	M12 or Early Term ⁵
Written informed consent	Х									
Medical history (MH)	Х	x*								Х
Physical examination (PE)	Х	x*								Х
Brief MH and PE				Х	X	Х	Х	х	Х	
Vital signs	Х	Х	Х	Х	X	Х	Х	х	Х	Х
Pregnancy test	Х	x*								Х
Safety laboratory tests ¹	Х	x*				Х	Х	х		Х
Urinalysis	Х	x*					Х	х		Х
Slit lamp and fundus exam	Х	Х		Х		Х	Х	х	Х	Х
Optos photography		Х		х		х	Х	х	Х	Х
BCVA (E-ETDRS)	х	Х	Х	х	х	х	Х	х	Х	Х
IOP		Х	Х	х	х	х	Х	х	Х	Х
OCT		Х								Х
VF		Х						х		Х
Exploratory Testing (optional) ⁶		Х			Х	Х	Х	Х	Х	Х
Contrast sensitivity		Х						Х		Х
Mobility test		Х						х		Х
Study Drug Injection			Х							
Con Meds			Х	Х	Х	Х	Х	Х	Х	Х
Adverse events			Х	Х	Х	х	Х	Х	Х	Х
Blood sample for Ab testing ²		Х				х		Х		

¹Hematology (minimally Hct, Hgb, CBC with diff, plt), coagulation panel (screening only) and blood chemistries (minimally AP, ALT, AST, BUN, Cr, total bilirubin, serum electrolytes, glucose, calcium, phosphate, albumin, total protein and HbA1c) ² Testing for Panel Reactive Antibodies (PRA) and Donor Reactive Antibodies (DRA)

³ visit window +/- 1 day ⁴ visit window +/- 4 days ⁵ visit window +/- 10 days

⁶ subjects may have some or all of the following assessments at the jCyte Low Vision Facility at the indicated timepoints: ultrasound imaging [ultrasound biomicroscopy (UBM), A-scan, and/or B-scan], slit lamp biomicroscopy with photography/videography using gonioscopy lens, OCT imaging of jCells, retinal sensitivity with FST of both eyes separately (monocular testing, FST only performed at Baseline, M3, M6, and M12) *Day -30 to 0. Does not need to be repeated if Day 0 is within 30 days of screening.

